**Aims 3, 4, and 5 pertain to all 210 participants randomized (n=105 to receive BATA and n=105 to receive MBCT).**

Aim 3: We predict that BATA will produce clinically and statistically significant improvements in anhedonia and functional outcomes that exceed those due to the comparison treatment.

Aim 4: We predict that BATA will improve behavioral indices of reward sensitivity.

Aim 5: To evaluate the effects of BATA versus a comparison treatment on neural response to rewards. We predict that, consistent with Aim 1, BATA will increase right CN activation during reward anticipation and decrease rACC activation during reward outcomes and that BATA will not decrease amygdala activation to threat, confirming the specificity of BATA for targeting these positive valence neural systems. This Aim will provide a replication and extension of Aim 1 findings with a larger sample and with an optimal treatment dose.

In the PET sub-study, Hypothesis 1- BATA, but not the comparison treatment, will result in increased phasic striatal DA release but will not influence background DA striatal tone. Hypothesis 2- that normalization of fMRI-derived mesocorticolimbic activation due to BATA specifically will be associated with increased phasic DA release but no change in background DA tone during incentive processing.

This is not a pilot study but rather a Phase I/II study. The R61 phase (Phase I) of the protocol is designed to provide preliminary data for the acceptability, identification of the optimal dose of BATA as well as the preliminary efficacy of BATA in subjects with anhedonia compared to those in the MBCT control group. Using the fMRI data, this phase of the study will test if BATA produces changes in neural responses to reward anticipation and reward outcomes that exceed changes in the MBCT group and does not impact neural responses to threat. As such, a small group (N = 60) of subjects will be in this blinded phase and they will complete up to a total of 4 fMRI scans (pre-treatment, week 8, 12 and post-treatment). The R61 study will be entering a no-cost extension at the end of the current project period to allow for completion of data collection for this phase. Due to limited funds, the number of scans obtained is being reduced from up to 4 scans to two scans (pre- and post-treatment.) for participants

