### **Study Visits:**

Potential participants will complete the following:

- 1) A phone or online screen to determine initial eligibility via UNC's REDCap

- 2) A 1-2 clinical characterization visit(s) to determine eligible, and, if eligible, to characterize participants clinically. During COVID, can be split remote/in-person.
- 3) A pre-treatment 7 Tesla (7T) fMRI scan & if one of the first 60 subjects enrolled, have an initial blood draw of 10ml (2tsp). Update, the NARSAD blood protocol had entered an extension and has additional funds so up to 210 participants, in both phases, will have an initial blood draw of 10ml (2tsp). **As of 6/26/20, the blood protocol will no longer continue for any new participant enrolled in the study. As of the NCE 2022, this current amendment, imaging of new participants will end. Only enrollment into the therapy portion at Duke will continue.**
- 4) Patients will then be assigned randomly to the experimental treatment (BATA) or comparison treatment (Mindfulness Based Cognitive Therapy (MBCT)) for approximately 15 weeks of treatment.
- 5) The first 60 patients enrolled (n=30 who receive BATA and n=30 who receive MBCT) will additionally complete two additional, mid-treatment, fMRI scans as well as an additional blood draw at all other MRI visits. The 1st phase of the study entered the R61 no cost extension at the end of the project period & due to limited funds, participants will no longer be receiving up to 4 scans. Participants who consent at UNC on or after 11/1/18 will receive only pre- and post-treatment scans (2 scans total). **The R61 no cost extension has ended and the study has entered the larger R33 phase of the study and participants will continue to receive only pre and post treatment scans (2 total) and no bloodwork will be collected starting summer 2020 for new participants. \*\*No new enrollment to imaging at UNC will occur with the approval of the June 2022 NCE amendment.**
- 6) A post-treatment clinical characterization visit
- 7) A post-treatment 7T scan

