### 6.4 STUDY INTERVENTION COMPLIANCE

A participant will be considered a drop if they miss 4 therapy sessions in a row. Up to two sessions per week can be conducted to make up previously missed weeks. No more than 4 sessions will be completed before week 4, no more than 7 sessions will be complete before week 7, no more than 11 sessions will be complete before week 11. At week 8 onward, clinical response WILL be assessed and discussed with participant to determine if therapy is complete or will continue. No Therapy sessions will be held in wk 16.

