**Aim 2:** We will analyze whether dose moderates treatment response via regression models that predict change in neural target (CN and dACC) activation from the number of sessions as an indicator of BATA dose. Hierarchical linear modeling where time-in-weeks is treated as a continuous variable nested within subject will provide parameter estimates of the linear, quadratic, and cubic functions for change over time in neural target engagement over the course of treatment. Standard evaluation (e.g., significant at  $p < .05$ ) will guide our selection of the most appropriate function. From these functions, we can estimate both the point in time where the change in target engagement is greatest and where it approaches 0, meaning minimal further improvement is anticipated. Although mid-treatment scans will occur at weeks 8 and 12, we will estimate change continuously so the optimal dosage is not restricted to one of those timepoints.

**Aims 3 and 4:** To evaluate the efficacy of BATA, relative to MBCT, for treating anhedonia, functional outcomes, and behavioral indices of reward sensitivity, we will test for differential change over time between those who receive BATA and those who receive MBCT post-treatment. We will use an intent-to-treat (ITT) analysis for patients who receive BATA relative to those who don't. The ITT model will be a repeated-measures ANCOVA with effects for treatment condition (BATA, MBCT), outcome measure (SHAPS, PRT, etc), time (pre-treatment, post- treatment) and their interactions. The interaction tests will assess mean differences at each time point as well as differences in the degree of change between the groups. This also provides tests of each group relative to their baseline scores. We will include gender and age as covariates in these models. \*\*We will also note any participants who were enrolled in the study and had PRT & EffRT reward tasks data omitted during COVID-19 times.

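### Aim 2 cannot locate a plateau before week 8, locates a later one with bias, and uses a session count that is partly set by response as its measure of dose

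*Combined protocol and SAP*

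**What the plan says.** Section 9.2 (Aim 2) describes two analyses. One is a hierarchical linear model in weeks that "will provide parameter estimates of the linear, quadratic, and cubic functions for change over time in neural target engagement". Significance at p < .05 "will guide our selection of the most appropriate function". From the chosen curve, "we can estimate both the point in time where the change in target engagement is greatest and where it approaches 0". The section adds that although the mid-treatment scans fall at weeks 8 and 12, "we will estimate change continuously so the optimal dosage is not restricted to one of those timepoints". The other is a regression of change in neural activation on the number of sessions, taken as BATA dose.

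On the data available, Section 4.1 says of the 60 R61 participants that "they will complete up to a total of 4 fMRI scans (pre-treatment, week 8, 12 and post-treatment". Section 9.1 gives the post-baseline scans as weeks 8, 12 and 16. The Study Visits list in Section 4.1 then cuts this back: "Participants who consent at UNC on or after 11/1/18 will receive only pre- and post-treatment scans (2 scans total".

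On what sets the number of sessions, Section 6.4 says: "At week 8 onward, clinical response WILL be assessed and discussed with participant to determine if therapy is complete or will continue". The week 8 row of the table in Section 6.1.2 repeats the rule alongside the mid-treatment MRI, so it does not read as confined to R33. The same table ties the final scan to the final session when treatment ends in weeks 10-11.

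Section 4.1 predicts a plateau once the best dose has been delivered, and Section 4.3 expects the modelling to yield the best number of sessions.

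**The concern.** Treating time as continuous does not create information between scans. With nothing scheduled from week 0 to week 8, the shape of the curve over the first half of treatment comes from the polynomial chosen and not from data. A cubic has four mean parameters for four scheduled times, so almost nothing is left to check its fit.

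The sessions regression has a different fault. If good responders tend to finish from week 8 and others continue, session count is in part a result of response. An association with neural change can then appear without any effect of dose.

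At stake is the main product of Aim 2: a reported week, or number of sessions, at which BATA's neural effect levels off.

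**Working it through.** **No plan figure to reproduce.** Section 9.1 groups Aims 1, 2 and 5 but calculates power for Aim 1 only. No power, precision or plateau threshold is given for Aim 2.

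**1. Plateau without noise.** Inputs: scans at weeks 0, 8, 12 and 16 (Sections 4.1 and 9.1), and a curve that rises in a straight line to 1 and then stays flat. If it levels off at week 2, 4, 6 or 8, the expected means are the same: 0, 1, 1, 1. No analysis of these four means can tell the cases apart.

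- Quadratic, least squares: slope term 0.17386, curvature -0.0071023. Zero slope at 0.17386 / (2 × 0.0071023) = week 12.2.
- Cubic, exact fit: 0.27083t - 0.0234375t² + 0.00065104t³. The derivative 0.27083 - 0.046875t + 0.0019531t² is zero at t = (0.046875 ± 0.009021) / 0.0039063, that is, weeks 9.7 and 14.3. The first is taken as the plateau.

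Repeating this for later plateaus:

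| True plateau | Means | Quadratic | Cubic |
|---|---|---|---|
| Week 8 or earlier | 0, 1, 1, 1 | 12.2 | 9.7 |
| Week 10 | 0, 0.8, 1, 1 | 14.5 | 14.0 |
| Week 12 | 0, 0.667, 1, 1 | 17.8 | 14.1 |

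**2. Plateau with noise.** Simulation, 1,500 runs per setting: 25 BATA participants with all four scans (25 complete per group, Section 9.1); effect 0.75 to 1.25, the range in Section 9.1, read as SD units; correlation between scans 0.35 to 0.7 (assumed; 0.35 is stated for SHAPS only); highest-order term with p < .05 kept; plateau taken as the first zero of the slope within 16 weeks. Rise-then-flat results:

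- True week 4 or 8: when a plateau is returned, its median is week 10.6 to 11.9 for either truth, with a 5th-95th percentile range of about 5 to 14.
- No plateau is returned in about 52-53% of runs at effect 0.75 and correlation 0.35, falling to about 2% at 1.25 and 0.7.
- True week 12: a plateau is returned in 22-48% of runs.
- If 12 of the 25 have two scans (assumed; the number is not stated), a plateau is returned in 31-34% of runs at 0.75 and 0.35 for true week 4 or 8.

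**3. Sessions regression with no dose effect.** Let r be the correlation of neural change with clinical response, and k the size of the correlation of clinical response with session count. If sessions relate to neural change only through response, the induced correlation has size ρ = r × k. Its sign is negative, because responders stop sooner. With n = 25, z = atanh(ρ) × √22, and the two-sided rejection rate at .05 is about Φ(z - 1.96) + Φ(-z - 1.96).

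| k | r = 0.3 | r = 0.5 | r = 0.7 |
|---|---|---|---|
| 0.5 | ρ 0.15, 11% | ρ 0.25, 22% | ρ 0.35, 40% |
| 0.75 | ρ 0.225, 19% | ρ 0.375, 46% | ρ 0.525, 78% |
| 0.95 | ρ 0.285, 28% | ρ 0.475, 68% | ρ 0.665, 96% |

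Simulation with response-driven stopping gives 19-28%, 46-69% and 79-98%, in line with k of about 0.75 to 0.95, and almost all rejections are negative. With k = 0.5, simulation gives about 10%, 22% and 40%. The documents give neither r nor k.

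**The case against.** Several points on the other side stand.

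- A reader might infer that the cubic is fully saturated. It is not. Scans may slip to weeks 9 or 13 (Section 6.1.2), finals may follow an early end, and participants who drop out before week 8 after at least one session are asked for a scan (Section 7.1). The extra times are few, however, and are driven by attendance, dropout or response.
- A reader might infer that scan spacing alone fixes the answer. After week 8 the quadratic zero does move with the truth (12.2, 14.5, 17.8). It is biased, not constant.
- A reader might infer that two-scan participants say nothing about curvature. They sharpen the baseline-to-post contrast: adding 13 of them to 12 with four scans cuts the quadratic standard error by about 3-6%. The cut was by consent date, so a mixed model can use them.
- The simulated rule is one implementation. Section 9.2 says that change approaches zero, with no threshold, and that p < .05 guides the choice of function. A smooth exponential approach never has zero slope, so runs with no root are not all failures of the plan. The result for plateaus up to week 8 does not depend on this, because the expected means are identical.
- Sessions also depend on attendance, make-up sessions and the rule on four missed sessions, so response sets dose only in part.

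The strongest point concerns consequences. Section 6.1.1 records that R33 duration stays at 8-15 weeks, and the go/no-go decision rests solely on the ROI analysis (Sections 9.2 and 9.2.2).

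**Conclusion.** The concern holds within limits. For a rise-then-flat curve, a plateau before week 8 cannot be located from the scheduled scans, and the fitted curve reports a later one (week 12.2 or 9.7). Between weeks 8 and 16 the estimate is biased and imprecise, not impossible. The claim that the answer is not tied to the scan weeks goes further than the design allows.

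The sessions regression can be significant with no dose effect, in about 19-28%, 46-69% and 79-98% of trials at correlations of 0.3, 0.5 and 0.7, and less often if response only weakly determines sessions. These rates rest on assumed correlations and an assumed stopping rule. A reader might expect the artefact to look like a benefit of more sessions. The sign is typically the reverse, so it could also mask a true dose effect.

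Nor do the documents support inferring that R33 treatment length was altered on this analysis. The consequence is for what Aim 2 can conclude and report.

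**What to change.** In Section 9.2, Aim 2:

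1. Drop the cubic term.
2. Report within-BATA change from baseline at each scan week with confidence intervals, with MBCT alongside as context. This keeps Aim 2's own question, which a BATA-versus-MBCT contrast would replace. Keep all participants, including those with two scans, in the mixed model.
3. Limit any plateau statement to the scanned range, week 8 onward, and give it an interval. State that a plateau before week 8 cannot be located, and delete the claim that the result is not restricted to the scan weeks.
4. Label the sessions regression descriptive, because the number of sessions depends on response as well as attendance.

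The cost is wording and a simpler model, with no new data and no change to treatment. The downside is that Aim 2 no longer yields a single, continuously estimated optimal-dose point.

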**Aims 3, 4, and 5 pertain to all 210 participants randomized (n=105 to receive BATA and n=105 to receive MBCT).**

**Aim 3:** To evaluate the effects of BATA versus an active comparison treatment on anhedonic symptoms and functional outcomes.

**Aim 4:** To evaluate the effects of BATA versus an active comparison treatment on behavioral indices of reward sensitivity.

**Aim 5:** To evaluate the effects of BATA versus a comparison treatment on neural response to rewards.

PET Aims specifically refer to the 30 subjects who consent to the optional PET sub-study:

**Aim 1 (PET):** To evaluate the effects of BATA, relative to a comparison treatment, on PET-derived measures of DA functioning during incentive processing. We hypothesize that BATA, but not the comparison treatment, will result in increased phasic striatal DA release but will not influence background DA striatal tone.

**Aim 2 (PET):** To evaluate relations between treatment-related changes in fMRI-derived mesocorticolimbic activation and PET-derived DA functioning in the BATA-treated group. We hypothesize that normalization of fMRI-derived mesocorticolimbic activation due to BATA specifically will be associated with increased phasic DA release but no change in background DA tone during incentive processing.

Exploratory Aims include the data from the EMA optional study: Passive location tracking (PLT) data during the period of EMA monitoring will be collected via the MetricWire app to allow us to compare distance traveled before and after both treatments as a secondary, exploratory measure of behavioral activation. Follow-up analyses will evaluate relations between motion tracking, behavioral, brain, and clinical measures of response to both treatments.

**Specific Aim 3 (EMA):** To evaluate if BATA, relative to a comparison treatment, produces improvements in real-world positive affect and the use of BATA skills. We hypothesize that BATA, but not the comparison treatment, will be associated with improvements in real-world positive affect and the use of BATA skills.

**Specific Aim 4 (EMA):** To evaluate relations between treatment-related changes in fMRI-derived mesocorticolimbic activation and real-world positive affect and the use of relevant BATA skills in the

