#### **6.1.2 DOSING AND ADMINISTRATION**

##### **MBCT/BATA Therapy Window Visits:**

Therapy sessions will be managed overall by calendar weeks, rather than trying to count days. This study is offering up to 15 weeks (as opposed to sessions) of treatment. Therapists will be instructed that they need to push to schedule at least one appointment per week, even if it's not on the same day of the week each week. The therapy portion of the study will follow this protocol:

Therapy Week	Procedures & Window
Week 0	The week the first MRI scan takes place. This "starts the clock" for both therapy and assessments
Weeks 1-3	Weekly therapy sessions. Sessions can start post-scan in week 0 if preferred; up to two sessions can be scheduled in a calendar week to make up missed sessions, with no more than three sessions completed by the end of week 3. Therapy content will not be skipped: for example, the content designated for Session 1 will be administered at the first therapy session, regardless of the week in which it takes place.
Week 4	Follow-up REDCap Questionnaires, computer tasks, and therapy. REDCap questionnaires and computer tasks will take place in this week as long as at least one session was attended in weeks 0-3. If 0 sessions were attended prior to this week, assessment is delayed to Week 5. If a subject has not attended at least one therapy session by the end of Week 4, they are a study drop by the 4-miss rule. This way every subject will have at least one "dose" (=therapy session) prior to the Wk4 visit.
Week 5	Weekly therapy session. If necessary, this can be a make-up for the Week 4 assessment if they did not attend or if Week 4 was first therapy session. If the participant does not attend therapy in Weeks 4 or 5, the "Wk4 Assessments" will not be collected and will be considered missing.
Weeks 6-7	Weekly therapy sessions. Up to two sessions per week can be conducted to make up previous missed appointments. No more than 7 Sessions will be delivered by the end of Week 7.
Week 8	Follow-up REDCap questionnaires, computer tasks, therapy, MRI Scan. If the subject has not attended at least 2 sessions overall, including at least 1 session in weeks 5-7, assessments and MRI scan may be delayed to Week 9. If a subject has not attended at least 1 session between weeks 5-8, they are a study drop by the 4-miss rule. Clinical response will be assessed and discussed with participants at this therapy session to determine if therapy is complete or will continue.

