### 6.3 MEASURES TO MINIMIZE BIAS: RANDOMIZATION AND BLINDING

Randomization assignment will be performed through a dynamic balancing protocol that will balance treatment assignment within groups of lower (20-30) and higher (31+) SHAPS scorers. We recognize that anhedonia is common in patients with major depression. To ensure a true transdiagnostic sample, we will monitor DSM diagnoses of enrolled subjects in both phases to ensure that no more than 40% in either phase meet DSM criteria for a current depressive episode. We will stratify groups based on SHAPS scores. **For the R33 phase**, we will no longer stratify groups based on SHAPS score as all participants will have SHAPS scores 30 or greater.

Unblinding does not apply to this study since study therapists and participants are aware of which group the participant is in for the therapy intervention.

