Exploratory Connectivity Analyses: Mesocorticolimbic connectivity in central to anhedonia. We will explore task-dependent correlations between ROIs using a psychophysiological interactions approach as in our prior work. Timeseries will be extracted from ROIs using FSL Featquery for each participant and trial type and correlation values will be transformed using a Fisher r-to z transformation. We also conduct whole-brain connectivity analysis, with a particular emphasis on the salience network (i.e., dorsal anterior cingulate cortex, anterior prefrontal cortex, and anterior insula), by segmenting the brain based on a probabilistic atlas, while correcting for multiple comparisons at the familywise error rate of  $p < .05$ .

**Secondary Analysis:** Secondary data analysis will be conducted examining relationship between psychological symptoms and patterns of brain activation in the functional neuro data. Data will be transferred from UNC to Duke to be analyzed by Duke study team members.

**Aims 1 and 5:** Only patients who complete baseline measures will receive BATA, and those who complete at least one BATA session will participate in post-treatment assessments (ITT, estimating ~90% of sample). We will compare fMRI activation in regions of interest at pre- and post-treatment. Primary analyses will address changes in regional brain activation from baseline to post-treatment.

Models will include motion parameters, gender, and age as covariates. The design is a 2 (BATA vs MBCT) X 3 (CN, rACC, amygdala) X 2 (pretreatment vs post-treatment) ANCOVA testing the change from pre- to post-treatment as moderated by treatment group and brain region in the outcome variables controlling for the covariates. Post-hoc comparisons will compare change across each region. Note that CN and rACC activation values are derived from the MID task whereas amygdala activation values are derived from the threat task.

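### The set labelled ITT is described by therapy received, and the plan never states that all randomised participants are analysed in their assigned arm

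*Combined protocol and SAP*

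**What the plan says.** Two sentences in section 9.2 carry the ITT label.

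- Aims 1 and 5: "those who complete at least one BATA session will participate in post-treatment assessments (ITT, estimating ~90% of sample". Only BATA is named; no matching condition is given for MBCT.
- Aims 3 and 4: "We will use an intent-to-treat (ITT) analysis for patients who receive BATA relative to those who don't". The model then follows: "The ITT model will be a repeated-measures ANCOVA with effects for treatment condition (BATA, MBCT" and further factors for outcome measure and time, with pre- and post-treatment as the two time points.

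Section 3 gives the intended scope: "Aims 3, 4, and 5 pertain to all 210 participants randomized (n=105 to receive BATA and n=105 to receive MBCT". Section 4.1 repeats it.

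Other sections decide who can reach the analysis.

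- Section 4.1, Study Visits, places randomisation after the pre-treatment scan and before therapy: "Patients will then be assigned randomly to the experimental treatment (BATA) or comparison treatment".
- Section 6.3 says that "study therapists and participants are aware of which group the participant is in for the therapy intervention".
- Section 6.1.2 applies to both therapies: "If a subject has not attended at least one therapy session by the end of Week 4, they are a study drop".
- Section 7.1 asks people who leave before 8 weeks to return for a final scan if they have had at least one session. The neuroimaging text in section 4.2 asks early drop-outs back for tasks, questionnaires and MRI, and states no session minimum.

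Section 9 names no method for participants who have a baseline value but no post-treatment value.

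**The concern.** An ITT analysis keeps every randomised participant in the assigned arm, whatever happens afterwards. Here the label is attached to a set that depends on attending a session, which is an event after randomisation. Because participants know their arm, whether they start may depend on which therapy they were given, and also on how they would have fared. If so, the starters in the two arms are no longer comparable by design, and a reader of the report would not know it, because the analysis would be called ITT.

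The Aims 3 and 4 contrasts, including SHAPS, are affected, as are the imaging contrasts of Aims 1 and 5. The stated scope of all 210 randomised participants would also not be delivered.

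**Working it through.** **1. The plan's own power figure.** Inputs from section 9.1: 65 completers per arm (N = 130), alpha 0.05, correlation 0.35, f = 0.2. For the group-by-time interaction with m = 2 time points, the noncentrality is f² × N × m / (1 − ρ), with 1 and 128 degrees of freedom.

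- f = 0.20: 0.04 × 130 × 2 / 0.65 = 16.0, power 97.8% (stated 98%).
- f = 0.14: 0.0196 × 130 × 2 / 0.65 = 7.84, power 79.4% (stated 80%).

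Both figures reproduce. They rest on completers, so they do not show who is in the ITT set.

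**2. How many people are involved.** The complement of about 90% is about 10%.

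- Whole sample: 0.10 × 210 = 21; in the first phase, 0.10 × 60 = 6.
- If the condition bound BATA alone: 0.10 × 105 = 10.5, or 5% of all randomised.

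The 90% is given for Aims 1 and 5. Carrying it to Aims 3 and 4 is an inference; it is reasonable because Aim 5 covers the same 210 people and the Week 4 drop rule applies to everyone. Other figures in the plan imply larger losses from all causes: 25 of 30 complete in Aim 1 (17% lost), 81% retention in section 5.4 (19% lost), and 65 complete against 105 randomised (38% fewer).

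**3. What leaving out non-starters does.** Let q be the share of an arm that does not start, and D how much worse its non-starters do, in SD of the analysed outcome. The all-randomised mean is (1 − q) × S + q × (S − D) = S − qD, where S is the mean of starters. The starter mean is therefore too favourable by qD, and the bias in the contrast is

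q(BATA) × D(BATA) − q(MBCT) × D(MBCT).

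It is zero when both q and D are equal across arms. The documents give neither by arm, so the following are **assumptions** chosen to show a range, with D the same in both arms:

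| Non-start, BATA vs MBCT | D = 0.25 | D = 0.5 | D = 1.0 |
|---|---|---|---|
| 10% vs 10% | 0 | 0 | 0 |
| 15% vs 5% | +0.025 | +0.05 | +0.10 |
| 5% vs 15% | −0.025 | −0.05 | −0.10 |

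Positive values favour BATA.

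For scale, take a simple two-sided 5% comparison of two means and shift it by bias / √(2/n). With the plan's 65 per arm, √(2/65) = 0.175. A bias of 0.05 SD then gives 5.9% error and 0.10 SD gives 8.8%. A more extreme assumption (2% vs 18%, D = 0.75) gives a bias of 0.12 SD and 10.5% error.

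**4. Whether redefining the set is enough.** Section 4.2 collects SHAPS during treatment at therapy visits, which non-starters do not attend. After the Week 4 drop they would have baseline only. With the plan's correlation of 0.35, baseline explains 0.35² = 12% of the variance of the post-treatment score. A likelihood-based model therefore corrects a difference in outcome only so far as it shows at baseline. Post-treatment values must also be sought.

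**5. Power after the fix.** Assume that the restored 10% are balanced, have no treatment effect and are measured, so that f shrinks by a factor of 0.9. With all 210 measured, power is 99.5% at f = 0.18 and 89.0% at f = 0.126. If the measured number rises only from 130 to 130/0.9 ≈ 144, power is 96.4% and 75.0%.

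**The case against.** The strongest reply is that this is loose wording. The protocol often uses receiving BATA to mean being allocated to it: section 3 speaks of participants randomised to receive each therapy, and section 4.1 counts the first 60 by the therapy they receive. The model factor is treatment condition with levels BATA and MBCT, and no crossover is described. This stands. A reader might infer from the Aims 3 and 4 sentence that the plan is an as-treated comparison in which a BATA non-starter is counted with MBCT. That rests on a literal reading of one sentence, and the model gives it no mechanism.

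A reader might also infer that the entry rule binds BATA only, so that one arm loses 10% and the other none. The working rules in sections 6.1.2 and 7.1 say therapy session without naming an arm, and this makes such a split unlikely.

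It can further be said that the Aims 1 and 5 sentence describes who is assessed, not who is analysed. That is partly right, but the sentence itself calls this set ITT. With a two-time-point model and no missing-data method, participants without a post-treatment value have no stated way into the analysis. Section 3's reference to all 210 randomised shows the intent; it does not supply the rule.

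**Conclusion.** The point holds as a defect in the definition of the analysis set. The plan ties its ITT label to therapy received and nowhere states that all randomised participants are analysed as assigned. Taken with the Week 4 drop rule, non-starters in both arms would probably be left out of an analysis reported as ITT.

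The count of about 21 of 210 assumes that the 90% applies to the whole sample and to all aims. Bias arises only if non-start rates or the prognosis of non-starters differ by arm. Open assignment makes that possible but does not establish it. The documents therefore do not support saying that randomisation's protection is lost in every contrast, nor any particular bias or error rate; the figures above only illustrate assumed inputs. Power is not the reason for the change.

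**What to change.** In section 9.2:

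1. Define the ITT set for Aims 1, 3, 4 and 5 as all randomised participants in their assigned arm, regardless of sessions attended.
2. Fit a likelihood-based model that includes participants with a baseline but no post-treatment value, and add a sensitivity analysis for missing outcomes.
3. Relabel the at-least-one-session set as modified ITT, apply it identically to both arms, and keep it as a sensitivity analysis. Describe the 90% as the share expected to be assessed.

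In the follow-up text, seek post-treatment self-report, including SHAPS, from all randomised participants. Section 4.2 already provides REDCap survey invitations by email. Reconcile the neuroimaging text in section 4.2, which states no session minimum for asking early drop-outs back, with section 7.1, which requires at least one. Also reconcile section 4.1, which calls the first phase blinded, with section 6.3.

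Scans cannot be recovered by survey, so for Aims 1 and 5 the missing-data sensitivity analysis carries more weight. State separately how participants enrolled after imaging closed under the June 2022 amendment are handled in Aim 5.

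The cost is a few sentences, a little more follow-up through existing surveys, and slight dilution of the estimate by people who received no therapy.
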